9. PRE-STUDY AND CONCOMITANT INTERVENTION/MEDICATION

Concomitant medications will be documented during screening and updated during the study. Disallowed medications and therapies are medications or therapies that contraindicate contact lens wear. See the Exclusion criteria for specific details.

10. DEVIATIONS FROM THE PROTOCOL

Investigator will notify study sponsor upon identification of a protocol deviation. Major protocol deviations must be reported to the sponsor within 24 hours after discovery of the protocol deviation. The Investigator will report deviations per IRB/IEC requirements. All deviations will be tracked and corrective actions implemented as appropriate.

If it becomes necessary for the Investigator to implement a deviation in order to eliminate an immediate hazard to the trial subject, the Investigator may implement the deviation immediately without notification to the sponsor. Within 24 hours after the implemented deviation, the Investigator must notify and provide the rationale to the Sponsor and, as required, the IEC/IRB.

11. STUDY TERMINATION

The occurrence of one or more Unanticipated Serious Adverse Device Effect (USADE), or any SAE where the relationship to study agent cannot be ruled out, may result in stopping further

dispensing of test article. In the event of a USADE or SAE, the Sponsor may unmask the treatment regimen for the subject(s) and will discuss this with the Investigator before any further subjects are enrolled.

The Sponsor will determine when a study will be stopped. The Principal Investigator always has the discretion to initiate stopping the study based on patient safety or if information indicates the study's results are compromised.

JJVC reserves the right to terminate the study at any time for any reason. Additionally, the IEC/IRB reserves the right to terminate the study if an unreasonable risk is determined. The study can be terminated by the Principal Investigator at the individual clinical site due to specific clinical observations, if in their opinion, after a discussion with JJVC, it is determined that it would be unwise to continue at the clinical site.

JJVC (and the IEC/IRB and DMC, if applicable) will evaluate all adverse events. If it is determined that an adverse event presents an unreasonable risk, the investigation, or that part of the investigation presenting the risk, will be terminated, as soon as possible.

Should the study be terminated (either prematurely or as scheduled), the Investigator will notify the IEC/IRB and Regulatory Authority as required by local regulatory requirements.

12. PROCEDURE FOR HANDLING PRODUCT QUALITY COMPLAINTS

A Product Quality Complaint (PQC) refers to any written, electronic, or oral communication that alleges deficiencies related to the identity, quality, durability, reliability, safety, effectiveness or performance of test articles after they have been released for clinical trial use.

Potential complaints may come from a variety of sources including but not limited to subjects, clinical research associates (CRA), clinical operations managers (COM), medical monitors, and site personnel, etc. The following are not considered product quality complaints:

- Subject satisfaction inquiries reported via “Subjective Questionnaires” and “Patient Reported Outcomes (PRO)”
- Clinical test articles that are stored improperly or damaged after receipt at the investigational site
- Lens replacements that occur due to drops/fall-outs
- Damage deemed by clinicians or clinical staff to be caused by handling by the user, and not indicative of a quality deficiency (i.e. tears, rips, etc.), only in situations where there is no deficiency alleged by the subject

Within 24 hours of site personnel becoming aware that a PQC has occurred, the PQC must be recorded in the EDC system, which will trigger an automatic email notification to the appropriate COM/CRA and Clinical QA representative. In cases where the EDC system in use is not configured to send automatic notifications or when an EDC system is not used, the COM/CRA is responsible for notifying Clinical QA upon discovery that a PQC has occurred.

Upon receipt of the EDC notification, the COM/CRA will contact the study site to collect additional information which will include:

- Date the complaint was received/recorded in the EDC System (Date of Sponsor Awareness)
- Who received the complaint
- Study number
- Clinical site information (contact name, site ID, telephone number)
- Lot number(s)
- Unique Subject Identifier(s)
- Indication of who first observed complaint (site personnel or subject)
- OD/OS indication, along with whether the lens was inserted
- Any related AE number if applicable
- Detailed complaint description (scheduled/unscheduled visit, wear time, symptoms, resolution of symptoms, etc.)
- Eye Care Provider objective (slit lamp) findings if applicable
- Confirmation of product availability for return (and tracking information, if available), or rationale if product is not available for return [REDACTED]

Once a complaint is received, it will be assessed by the COM, CRA, or trained site personnel to determine if it is an Adverse Event/Serious Adverse Event (AE/SAE). If the complaint results in an AE/SAE, the COM/CRA, or trained site personnel will follow Section 13 of this protocol. If the AE/SAE was potentially the result of a product quality related deficiency, these procedures also applies and will be executed in parallel.

In some cases, a PQC form may be generated in EDC by the site in error. In this event, the PQC forms will be marked “Intentionally Left Blank” or “ILB”. Justification for ILB must be documented.

13. ADVERSE EVENTS

13.1. Definitions and Classifications

Adverse Event (AE) – An AE is “any untoward medical occurrence, unintended disease or injury, or untoward clinical signs (including abnormal laboratory findings) in subjects, users or other persons, whether or not related to the investigational medical device.

Note 1 to entry: This definition includes events related to the investigational medical device or the comparator.

Note 2 to entry: This definition includes events related to the procedures involved.

Note 3 to entry: For users or other persons, this definition is restricted to events related to investigational medical devices.”¹

An AE includes any condition (including a pre-existing condition) that:

1. Was not present prior to the study, but appeared or reappeared following initiation of the study
2. Was present prior to the study, but worsened during the study. This would include any condition resulting from concomitant illnesses, reactions to concomitant medications, or progression of disease states
3. Pregnancy must be documented as an adverse event and must be reported to the clinical monitor and to the Sponsor immediately upon learning of the event

Serious Adverse Event (SAE) – An SAE is any untoward medical occurrence that:

- Results in death
- Is life threatening
- Requires in-patient hospitalization or prolongation of existing hospitalization
- Results in persistent or significant disability/incapacity (e.g., a sight threatening event, a significant persistent or permanent change, impairment, damage, or disruption to the subject's body)
- Is a congenital anomaly/birth defect
- Requires intervention to prevent permanent damage (the use of the test article resulting in a condition which requires medical or surgical intervention to preclude permanent impairment of the body structure or a body function). Important medical events that may not result in death, be life-threatening, or require hospitalization may be considered an SAE when, based upon appropriate medical judgment, they may jeopardize the patient or subject and may require medical or surgical intervention to prevent one of the outcomes listed in the above definition

Diagnoses and conditions that are considered Ocular Serious Adverse Events include, but not limited to:

- Microbial Keratitis (MK)
- Iritis (including cells in the anterior chamber)
- Permanent decrease in best spectacle corrected visual acuity equivalent to 2 acuity lines or greater
- Central Corneal Opacity
- Central Corneal Neovascularization
- Uveitis
- Endophthalmitis
- Hypopyon
- Hyphemia
- Penetration of Bowman's Membrane
- Persistent Epithelial Defect
- Limbal cell Damage leading to Conjunctivalization

Significant Adverse Events – Those events that are usually symptomatic and warrant discontinuation (temporary or permanent) of the test article (excluding Serious Adverse Events).

Diagnoses and conditions that are considered Ocular Significant Adverse Events include, but not limited to the following:

- Contact Lens Induced Peripheral Ulcer (CLPU)
- Significant Infiltrative Events (SIE)
- Superior Epithelial Arcuate Lesions (SEALs)
- Any Temporary Loss of > 2 Lines of BSCVA
- Other grade 3 or higher corneal findings, such as abrasions or edema
- Non-contact lens related corneal events - e.g. Epidemic Keratoconjunctivitis (EKC)
- Asymptomatic Corneal Scar
- Any corneal event which necessitates temporary lens discontinuation > 2 weeks

Non-Significant Adverse Events – Those conditions that are usually asymptomatic and usually do not warrant discontinuation (temporary or permanent) of the test article. However, the Investigator may choose to treat as a precautionary measure.

Diagnoses and conditions that are considered Ocular Non-Significant Adverse Events include, but not limited to the following:

- Non-significant Infiltrative Event (NSIE)
- Contact Lens Papillary Conjunctivitis (CLPC)
- Superficial Punctate Keratitis (SPK)
- Conjunctivitis: Bacterial, Viral, Allergic
- Blepharitis
- Meibomianitis
- Contact Dermatitis
- Localized Allergic Reactions
- Any corneal event not explicitly defined as serious or significant adverse event, which necessitates temporary lens discontinuation < 2 weeks

Adverse Device Effect (ADE) – An ADE is an “adverse event related to the use of an investigational medical device.

Note 1 to entry: This definition includes adverse events resulting from insufficient or inadequate instructions for use, deployment, implantation, installation, or operation, or any malfunction of the investigational medical device.

Note 2 to entry: This definition includes any event resulting from use error or from intentional misuse of the investigational medical device.”¹

Unanticipated Adverse Device Effect (UADE) – Any serious adverse effect on health or safety or any life-threatening problem or death caused by, or associated with, the test article, if that effect, problem, or death was not previously identified in nature, severity, or degree of incidence in the investigational plan, Investigator’s Brochure or protocol, or any other unanticipated serious problem associated with the test article that relates to the rights, safety and welfare of subjects.

13.2. Assessing Adverse Events

In conjunction with the medical monitor, the Investigator will evaluate adverse events to ensure the events are categorized correctly. Elements of categorization will include:

- Seriousness/Classifications (see definition in Section 13.1)
- Causality or Relatedness – i.e. the relationship between the test article, study treatment or study procedures and the adverse event (not related; unlikely related; possibly related; related - see definition in Section 13.2.1)
- Adverse Event Severity – Adverse event severity is used to assess the degree of intensity of the adverse event (mild; moderate; severe for all events - see definition in Section 0)
- Outcome – not recovered or not resolved; recovering or resolving; recovered or resolved with sequelae; recovered or resolved; death related to adverse event; unknown
- Actions Taken – none; temporarily discontinued; permanently discontinued; other

13.2.1. Causality Assessment

Causality Assessment – A determination of the relationship between an adverse event and the test article. The test article relationship for each adverse event should be determined by the investigator using these explanations:

- Not Related- An adverse event that is not related to the use of the test article, study treatment or study procedures
- Unlikely Related – An adverse event for which an alternative explanation is more likely, e.g. concomitant treatment, concomitant disease(s), or the relationship of time suggests that a causal relationship is not likely
- Possibly Related – An adverse event that might be due to the use of the test article, or to the study treatment or study procedures. An alternative explanation, e.g. concomitant treatment, concomitant disease(s), is inconclusive. The relationship in time is reasonable. Therefore, the causal relationship cannot be excluded
- Related – An adverse event that is listed as a possible adverse effect (device) or adverse reaction (drug) and cannot be reasonably explained by an alternative explanation, e.g. concomitant treatment of concomitant disease(s). The relationship in time is very suggestive, e.g. it is confirmed by de-challenge and re-challenge

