13.4.1. Reporting Adverse Events to Sponsor

Serious/Significant Adverse Events

The Investigator will inform the sponsor of all serious/significant adverse events occurring during the study period as soon as possible by e-mail, fax, or telephone, but no later than 24 hours following discovery of the event. The Investigator is obligated to pursue and obtain information requested by the Sponsor in addition to that information reported on the eCRF. All subjects experiencing a serious/significant adverse event must be followed up and all outcomes must be reported.

When medically necessary, the Investigator may break the randomization code to determine the identity of the treatment that the subject received. The Sponsor and study monitor should be notified prior to unmasking the test articles.

In the event of a serious/significant adverse event, the Investigator must:

- Notify the Sponsor immediately
- Obtain and maintain in the subject’s records all pertinent medical information and medical judgment for colleagues who assisted in the treatment and follow-up of the subject
- Provide the Sponsor with a complete case history which includes a statement as to whether the event was or was not related to the use of the test article
- Notify the IEC/IRB as required by the IEC/IRB reporting procedure according to national regulations

Unanticipated (Serious) Adverse Device Effect (UADE)

In the event of an Unanticipated (Serious) Adverse Device Effect (UADE), the Investigator will submit a report of the UADE to the Sponsor and IEC/IRB as soon as possible, but no later than 24 hours after the Investigator first learns of the effect. This report is in addition to the immediate notification mentioned above.

The Sponsor must conduct an evaluation of the UADE and must report the results of the evaluation to FDA, the IEC/IRB and participating Investigators within 10 working days after the Sponsor first receives notification of the effect.

Non-Serious Adverse Events

All non-serious adverse events, including non-serious adverse device effects, will be reported to the sponsor by the Investigator no later than 2 days from discovery.

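### The adverse-event item labelled as relationship to the test article also counts study procedures as causes, so on its own it cannot separate lens-caused from procedure-caused events

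*Combined protocol and SAP*

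**What the plan says.** Section 13.2.1 introduces the causality assessment as "A determination of the relationship between an adverse event and the test article", and instructs: "The test article relationship for each adverse event should be determined by the investigator using these explanations". Four categories follow. *Not Related* is "An adverse event that is not related to the use of the test article, study treatment or study procedures". *Possibly Related* begins "An adverse event that might be due to the use of the test article, or to the study treatment or study procedures", and adds that an alternative explanation is inconclusive and the timing reasonable. *Unlikely Related* applies when another explanation is more probable, with concomitant treatment or disease as examples. *Related* requires a listed device effect or drug reaction with no other reasonable explanation.

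The surrounding sections do not agree on what is being rated:

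- Section 13.2 describes relatedness as covering the test article, the study treatment and the study procedures together. The follow-up text in Section 13.3 and the ethics-committee report in Section 13.4 use the same three-part scope.
- The documentation list in Section 13.3 asks for relationship to the test articles only, and separately for the likely etiology.
- Section 13.1 defines an ADE as an "adverse event related to the use of an investigational medical device", and a UADE as a serious effect caused by or associated with the test article.
- For serious or significant events, Section 13.4.1 asks for "a statement as to whether the event was or was not related to the use of the test article".

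**The concern.** The label on the item and the definitions used to fill it in refer to different sets of causes. The trial uses procedures that can themselves cause ocular events; fluorescein, mentioned at the slit-lamp steps, is the obvious one. Section 13.1 states that events related to procedures are adverse events, so they will be recorded and must be rated. If the only causality rating described merges the causes, a reaction to a procedure can be filed as possibly related to the lens.

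What is at stake is how lens-related events are attributed for an investigational device. The study has a single arm, so no comparator group could reveal that an event was assigned to the wrong cause. Few lens-related events are expected, so one misfiled event would be visible in any summary of device effects.

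**Working it through.** The plan gives no figure to reproduce. The check is textual, with a short illustration of scale.

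**Step 1. Is a procedure-only event recordable?** Section 13.3 starts adverse-event recording at exposure to the test article, the study treatment or a study procedure. Section 13.1 includes procedure-related events. In Section 7.2, step 1.18 (slit lamp) refers to clearing fluorescein, and the first lens goes in at step 1.21. A fluorescein reaction at step 1.18 is therefore recordable, and the study lens cannot have caused it. Section 13.3 also sends events reported before the test article, treatment or procedures to medical history. By step 1.18 procedures have begun, so the recording rule governs. Even on the other reading, the question returns at steps 2.25 and 3.14.

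**Step 2. Put that event through the four categories of the test-article item.**

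| Category | Is it open to an event caused only by a procedure? |
|---|---|
| *Not Related* | No. The wording excludes any event related to study procedures. |
| *Unlikely Related* | Arguable, if the procedure is taken as the more probable alternative explanation. The examples given are causes outside the study, and the category does not name the cause being rated. |
| *Possibly Related* | Its first sentence is met by a possible procedure cause alone. The later conditions on alternatives and timing depend on which cause is being rated. |
| *Related* | Only if the event is a listed effect or reaction. |

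The one category that correctly describes the lens relationship is closed. Two investigators could reasonably choose different categories from those left.

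**Step 3. Compare with how device effects are defined.** ADE and UADE depend on the device alone. No section says how either is derived from the rating, and Section 14.1 plans only general summaries of safety variables. If the merged rating is used, error for procedure-only events runs towards too many ADEs.

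**Step 4. Scale, for illustration.**

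- Exposures, assuming fluorescein in both eyes at all three scheduled slit-lamp examinations: 3 × 2 × 36 = 216 to 3 × 2 × 40 = 240 eye exposures. Of these, 2 × 36 = 72 to 2 × 40 = 80 occur at step 1.18, before any lens. These are exposures, not events.
- Zero events in 40: exact upper 95% limit 1 − 0.025^(1/40) = 0.088, so 0 to 8.8%.
- One event in 40: 2.5%. The lower limit is 1 − 0.975^(1/40) = 0.0006. The upper limit solves (1 − p)^40 + 40p(1 − p)^39 = 0.025, giving p = 0.132. The interval is 0.06 to 13.2%.
- Earlier studies in Section 1.5: 57 + 19 + 89 + 67 + 62 = 294 completers, plus one subject who left with lens-related ocular events, so about 1/295 = 0.3%. Those summaries report no procedure reaction.

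**The case against.** The best defence is that the combined scope is intended. Sections 13.2, 13.3 and 13.4 all use the three-cause phrase, and one inclusive rating is a conservative choice. On that view only the lead sentence of Section 13.2.1 is wrong. This has force, but it does not settle the matter: the documentation list in Section 13.3 and the ADE and UADE definitions would still need a lens-only answer, and no routine item is described that gives one for non-serious, non-significant events.

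Several stronger conclusions that a reader might draw are not supported:

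- *That procedure-only events must be rated at least Possibly Related.* *Unlikely Related* is arguably available, because its examples are not exhaustive and *Possibly Related* also needs the alternatives to be inconclusive.
- *That ADEs cannot be counted correctly, or that the causes can never be separated afterwards.* No section derives ADEs from this rating alone. Section 13.3 also records likely etiology, onset time and a full description. Section 13.2 involves the medical monitor in categorisation. Serious and significant events carry the lens-specific statement in Section 13.4.1. The eCRF layout is not in the documents and may hold separate fields.
- *That a misrated procedure reaction would set off the Section 11 provision on further dispensing.* That text concerns an unanticipated serious device effect or "any SAE where the relationship to study agent cannot be ruled out"; it is discretionary and does not cite the Section 13.2.1 rating. Section 13.1 lists localized allergic reactions as non-significant.
- *That reactions to the rewetting drops are caught in the same way.* This requires treating the drops as study treatment. Section 4.1 describes one study treatment, Section 5.1 assigns every subject the same test article, and Section 6.2 lists the drops as ancillary.

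**Conclusion.** The point holds in limited form. The item is labelled as relationship to the test article, yet as worded it denies *Not Related* to an event caused only by a procedure, including one that precedes any lens. The rating alone therefore cannot separate lens-caused from procedure-caused events, and an ADE count based on it may be too high. The exposure is mainly in non-serious, non-significant events, because serious and significant ones have a separate lens-specific statement.

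The expected effect is small. The documents give no procedure-reaction rate, so the number of affected events cannot be estimated, and the shift from 0/40 to 1/40 shows only what a single such event would do. Acuity and CLUE vision scores are untouched, and the plan has no safety hypothesis. The conclusion assumes that ADEs would be counted from this rating and that the eCRF has no separate procedure item; the documents settle neither. It is still worth correcting: sections of the same protocol disagree on what one field measures, and the correction is cheap.

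**What to change.** Reconcile Sections 13.2, 13.2.1 and 13.3 by rating two items on the existing four-level scale:

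1. Relationship to the test article, with definitions that name only the test article.
2. Relationship to study procedures or ancillary products, with definitions that name only those.

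State in Section 13.1 or 13.2.1 that ADE and UADE classification uses the first item, and add the second to the documentation list in Section 13.3. Where Sections 13.3 and 13.4 refer to all three causes, say that both items are meant. Define study treatment as the lens, or drop the term from the definitions, since the plan describes one treatment and one test article. If the eCRF already holds separate fields, the protocol need only say so and align its definitions.

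The cost is one extra eCRF field, a few sentences of protocol text, and one more judgement per event for the investigator.
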